### 4.5.3. Other Patient Reported Outcomes

Patient reported outcomes focused on quality-of-life and psychosocial measurements listed below at each scheduled visit as well as the change from Baseline to Week 17 will be summarized using the Full Analysis Set with descriptive statistics defined in Section 4.1:

[REDACTED]

[REDACTED]

[REDACTED]

[REDACTED]

## 4.6. Safety Analyses

All safety analyses, summaries, listings, and figures will use the Safety Analysis Set unless otherwise specified. All missing safety assessments will not be imputed unless otherwise specified. Imputation rules for incomplete or missing dates are provided in Section 6.

### 4.6.1. Extent of Exposure

Duration of exposure, in days, in each study period is calculated as follows:

Date of last dose of study intervention of study period – date of first dose of study intervention in study period + 1.

Temporary dosing interruptions are not taken into account for the duration of exposure.

The exposure information relative to the designated study period will be summarized using descriptive statistics as well as counts and percentages, as appropriate. The exposure information will be summarized overall and by actual treatment groups. Exposure summaries will be based on data collected by the study drug administration eCRF and data collected in the IRT.

#### Derivations and Definitions:

Compliance with study intervention, as a percentage, is calculated as ratio of the number of capsules taken by the participant during the study period or study divided by the number of capsules that should have been taken by the participant during the study or study period (including missed or incorrect doses), multiplied by 100.

For any participant who fails to return one or more dispensed drug kits, the compliance calculation will only be derived for the dispensed drug kits that are returned. Dispensation drug kit visit will be assigned to the returned drug kit irrespective of return date. For any participants the study intervention dispense date will be used to impute the missing or partial missed/incorrect dose date.

The overall compliance is derived by taking each participant's whole treatment duration into consideration when deriving the expected amount taken using the first and last dose date. And only dispensation visits with valid return records will be counted into overall compliance calculation.

#### Exposure Summaries:

The total duration of exposure to study treatment, actual duration of exposure to study treatment will be summarized for Dose Titration and Optimization Period (Weeks 1 to 5) and Maintenance Period (Weeks 6 to 17) respectively, number of dose adjustments in DTOP (Weeks 1 to 5), the average daily dose of study treatment will be summarized for MTP (Weeks 6 to 17).

Treatment compliance will be summarized and categorized as (<75%, 75% to 100%, >100%) for both DTOP (Weeks 1 to 5) and MTP (Weeks 6 to 17) and Overall.

#### Exposure Listings:

All exposure data will be listed, including date of first and last dose, total duration of exposure, total duration of actual exposure and average daily dose.

Treatment compliance data will also be listed to show details of the accumulated amount of study drug dispensed, returned, and expected to be taken during the DTOP (Weeks 1 to 5), MTP (Weeks 6 to 17) and overall, the corresponding compliance rate will be calculated and listed.

#### **4.6.2. Adverse Events**

All reported adverse events (AEs) will be coded by system organ class (SOC), preferred term (PT) using MedDRA version 27.0. The investigator will assess the relationship of an AE to study treatment, and an AE with a missing relationship to study treatment will be reported as related in the summaries. Severity, as determined by the investigator, will be classified as mild, moderate, severe, life-threatening, or fatal. An AE with missing severity will be reported as missing in the summaries.

All AEs will be summarized by counts and percentages, and summaries will be provided by actual received treatment across all study period as well as by DTOP (Weeks 1 to 5), and MTP (Weeks 5 to 17), respectively.

Note that participants who acquire COVID-19 or report AEs due to the COVID-19 public health emergency (e.g., anxiety) while on study will be coded accordingly and included in the AE summaries.

#### **Derivations and Definitions:**

AEs will be collected and reported from the start of study treatment up to the Safety Follow-up visit (approximately 14 days after the last dose of study treatment).

A treatment-emergent adverse event (TEAE) is defined as any AE that began on or after the first dose of study treatment until up to 14 days after the last dose of study treatment.

Adverse events of special interest (AESI) are AEs that are of scientific and medical concern specific to JZP385, which includes hallucination, and syncope. The groupings are defined using MedDRA terms, SMQs (standardized MedDRA queries) and PTs.

Time of first onset of AE is calculated as: TEAE start date – First dose date + 1 and is categorized as:

- Week 1 and 2 ( $1 \leq \text{day of first onset of AE} \leq 14$ )
- Week 3 ( $15 \leq \text{day of first onset of AE} \leq 21$ )
- Week 4 ( $22 \leq \text{day of first onset of AE} \leq 28$ )
- Week 5 ( $29 \leq \text{day of first onset of AE} \leq 35$ )
- Weeks 6 – 17 ( $36 \leq \text{day of first onset of AE} \leq 119$ )
- > Week 17 ( $120 \leq \text{day of first onset of AE}$ )

Incomplete AE start/stop date will be imputed according to Section 6.1.

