Tremor may have a pathophysiology different from other motor symptoms ([Helmich, 2012](#)). First, tremor does not progress as quickly as bradykinesia, rigidity, gait, and balance ([Louis, 1999](#)). Second, tremor severity does not correlate with the severity of other motor symptoms ([Louis, 2001](#)). Third, tremor can occasionally impact the body contralateral to the otherwise most affected side, ie, where bradykinesia and rigidity are most prominent. Finally, tremor responds less well to dopaminergic treatment than bradykinesia and rigidity ([Koller, 1994](#); [Fishman, 2008](#)). While the clinical presentation of tremor can be different, there is evidence to suggest that the underlying pathophysiology of ET and tremor in PD is similar ([Filip, 2022](#)). As a result, the proof-of-concept findings from a phase 2, randomized, double-blind, multicenter, placebo-controlled, dose titration study of suvecaltamide in adults with ET (Study CX-8998-CLN2-001 [T-CALM]), provide some support for the study of tremor in PD. The results of the 4-week T-CALM demonstrated that reduction in tremor with daily doses of 16 and 20 mg suvecaltamide is observed within several weeks, although the durability of the effect is unknown. In the T-CALM study, doses were titrated for the first 2 weeks and the

final target dose was maintained for 2 additional weeks; efficacy assessments were taken at the end of Weeks 2 and 4. Despite not meeting statistical significance on the primary endpoint (TETRAS-PS, as rated by independent video raters), numerical improvements favoring suvecaltamide over placebo were observed on TETRAS-PS as rated by the investigators at both timepoints. Numerical improvements were also observed on the TETRAS-ADL subscale at both timepoints. The 12-week Maintenance Period in the present study is of sufficient duration to permit assessment of the durability of efficacy of suvecaltamide for the treatment of moderate to severe residual tremor in PD.

From a safety perspective, AEs in the T-CALM study were primarily reported during the first week of treatment. Most of the commonly reported AEs resolved within a week of treatment initiation despite continued dosing with suvecaltamide. The 17-week treatment duration of the present study, with multiple clinic visits to assess safety as well as phone visits for AE reporting, will allow for adequate assessment of safety.

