##### 4.1.1.3. Period Start and End Date

Data summary and analysis will be provided for the following periods:

- Dose Titration and Optimization Period (DTOP) – Weeks 1 to 5

For analysis of visit-based safety assessments (lab results, vitals, ECGs, etc.), this period starts on the day of Baseline (the day of last assessment before the first dose date) and ends on either: 1)

the day of first dose in the Maintenance Period (Week 6) after the completion of Week 5 assessments; or 2) the day of the Early Discontinuation (E/D) visit on or prior to Week 5; or 3) the last contact (known) day if the participant is lost to follow-up prior to Week 5.

For analysis of occurrence-based safety assessments (AEs, concomitant medications, etc.), this period starts on the day of first dose of study intervention (Day 1) and ends on either: 1) the day prior to the first dose in the Maintenance Period; or 2) the last dose day on or prior to Week 5 if the participant early discontinued study treatment; or 3) the last contact (known) day if the participant is lost to follow-up prior to Week 5.

- Maintenance Period (MTP) – Weeks 6 to 17

For analysis of visit-based safety assessments (laboratory results, vitals, ECGs, etc.), this period starts on the day after the first dose of study treatment in the MTP at Week 6 and ends on either: 1) the day of Week 17 visit; or 2) the day of E/D visit on or prior to Week 17; or 3) the last contact (known) day if the participant is lost to follow-up prior to Week 17.

For analysis of occurrence-based safety assessments, this period starts on the day of first dose of study treatment in the MTP at Week 6 and ends on the last dose date on or prior to Week 17 if the participant enters the MTP.

- Safety Follow-up Period (SFUP) – 2 weeks after the last dose of study treatment

This period starts on the day after either 1) the Week 17 visit or the E/D visit (visit-based assessments) or 2) last dose date (occurrence-based assessments) and ends on the day the Safety Follow-up visit completes.

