#### **Adverse Events Summaries:**

A general overall summary of AEs with the number and percent of study participants who experienced the following types of events will be provided:

- Any TEAE
- Any treatment related TEAE
- Any serious TEAE

- Any TEAE by severity
- Any TEAE leading to permanent study treatment discontinuation
- Any TEAE leading to dose reduction
- Any TEAE leading to dose increase
- Any TEAE leading to dose interruption
- Any AESI

In addition, incidence of AEs will be further summarized by:

- TEAEs by SOC and PT
- TEAEs by PT
- Most common (5% in any arm) TEAEs by SOC and PT
- Most common (5% in any arm) TEAEs by PT without regard to SOC
- Treatment-related TEAEs by SOC and PT
- TEAEs by maximum severity, SOC, and PT
- Serious TEAEs by SOC, and PT
- TEAEs leading to permanent study treatment discontinuation by SOC, and PT
- TEAEs leading to dose increase, reduction and interruption by SOC, and PT
- TEAE by Time of First Onset, SOC, and PT
- AESIs by PT

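### The AE time-of-first-onset table counts days from first dose only and gives no number at risk, so most off-drug onsets of early stoppers land in the Week 1–17 bins (minor, cheap to fix)

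*SAP*

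**What the plan says.** SAP 4.6.2 (Adverse Events, Derivations and Definitions) gives this definition of a treatment-emergent event: "any AE that began on or after the first dose of study treatment until up to 14 days after the last dose of study treatment". The onset clock in the same subsection uses the first dose only: "Time of first onset of AE is calculated as: TEAE start date – First dose date + 1 and is categorized as". The bins are Days 1–14, 15–21, 22–28, 29–35, 36–119, and 120 onward. They feed one planned output, "TEAE by Time of First Onset, SOC, and PT".

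For the statistics, SAP 4.6.2 asks for counts and percentages and states no denominator per onset bin. SAP 4.6 makes the Safety Analysis Set the default for safety outputs.

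SAP 4.1.1.3 has a separate rule for occurrence-based data such as adverse events. The titration period ends at the last dose for someone who stops early, and the Safety Follow-up Period starts on the day after the "last dose date (occurrence-based assessments) and ends on the day the Safety Follow-up visit completes". That rule is not applied to the onset bins.

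**The concern.** The onset table is the finest planned view of when adverse events begin. It has two weaknesses.

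First, it treats the same kind of event differently by participant. Take a last dose on Day 20 and a first onset on Day 30: the table counts it in Week 5, although the participant has been off drug for ten days. A completer whose event starts ten days after a Day 119 last dose is counted after Week 17. If one arm has more early stopping, more off-drug time enters its early bins.

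Second, the bins differ twelvefold in length and the table does not show how many people were still on treatment and event-free when each bin opened. A reader who compares percentages across bins would see time trends produced by bin length and dropout. At stake is the reading of the safety time course, not any hypothesis test.

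**Working it through.** **Inputs.** Bin limits and the 14-day tail: SAP 4.6.2. Period rule: SAP 4.1.1.3. Planned treatment of 17 weeks, hence Day 119: SAP 1.2.1. Per-arm size: SAP 5. The onset table has no planned figure of its own. The sample size that supplies the denominators reproduces: 64 / (1 − 0.20) = 80 per arm, and a two-sample t-test with 64 per arm, difference 3.0 and SD 6.0 has 80.1% power.

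**1. Where off-drug days fall.** For last dose on Day L, the off-drug treatment-emergent days are L+1 to L+14.

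| Last dose | Bins that receive the 14 off-drug days |
|---|---|
| Day 7 | 7 in Weeks 1–2, 7 in Week 3 |
| Day 14 | 7 in Week 3, 7 in Week 4 |
| Day 28 | 7 in Week 5, 7 in Weeks 6–17 |
| Days 35 to 105 | 14 in Weeks 6–17 |
| Day 112 | 7 in Weeks 6–17, 7 after Week 17 |
| Day 119 (completer) | 14 after Week 17 |

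Up to L = 105, L+14 ≤ 119, so all 14 days fall in Week 1–17 bins. For L = 106 to 118, between 13 days and 1 day do. Averaged over L = 1 to 118, the share is 13.23 / 14 = 94.5%. A completer whose last dose falls on Day 116, within the visit window, would have 3 off-drug days in Weeks 6–17.

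**2. Size of the mixing.** Assume 16 of 80 stop drug early (80 − 64, reading the planned dropout as treatment stops), all 80 are dosed, and each stopper is followed for 14 days. Share per bin = off-drug days / (off-drug + on-drug days). Example, Week 3 with stops uniform over Days 3–35: off-drug 16 × 95/33 = 46.1; on-drug 16 × 126/33 + 64 × 7 = 509.1; share 46.1 / 555.2 = 8.3%.

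| Bin | Stops uniform, Days 1–118 | Stops uniform, Days 3–35 | All stop on Day 14 |
|---|---|---|---|
| Weeks 1–2 | 1.1% | 2.9% | 0% |
| Week 3 | 2.4% | 8.3% | 20.0% |
| Week 4 | 2.4% | 8.9% | 20.0% |
| Week 5 | 2.4% | 9.3% | 0% |
| Weeks 6–17 | 2.7% | 0.9% | 0% |

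The 20% is (16 × 7) / (80 × 7) = 112 / 560.

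**3. Effect of bin length.** Assume a constant daily hazard with 50% affected by Day 133: λ = ln 2 / 133 = 0.00521. A bin covering Days a to b shows exp(−λ(a−1)) − exp(−λb) of all participants.

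| Bin | Length (days) | Percentage shown |
|---|---|---|
| Weeks 1–2 | 14 | 7.0% |
| Week 3 | 7 | 3.3% |
| Week 4 | 7 | 3.2% |
| Week 5 | 7 | 3.1% |
| Weeks 6–17 | 84 | 29.5% |

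Risk never changes, yet Weeks 6–17 show about nine times the Week 5 figure.

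**4. Effect of the denominator.** With 16 early stops, the number on drug at Day 36 lies between 64 (all stopped by Day 35) and 75.3 (stops uniform over Days 1–118). Dividing by 80 understates the Weeks 6–17 percentage by a factor of 80/64 = 1.25 or 80/75.3 = 1.06. For example, 8/80 = 10.0% against 8/64 = 12.5%.

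**The case against.** Most of the case on the other side stands, and it limits the point.

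- **Other views over time exist.** A reader might infer that this is the only table of adverse events over time. It is not. SAP 4.6.2 also plans summaries by titration and maintenance period, SAP 4.1.1.3 lists the Safety Follow-up Period among the periods to be summarised, and Protocol 9.4.5 plans summaries by study period as well as by time of onset.
- **No contradiction.** The bins are named by week, and nothing says that they hold on-drug time only. Study day and study period are two derivations. The result is inconsistent handling of off-drug events, not two conflicting rules.
- **No predicted first-week cluster.** Protocol 4.2 says that "AEs in the T-CALM study were primarily reported during the first week of treatment". A reader might take this as a forecast that merging Weeks 1 and 2 would hide. It is a result from an earlier 4-week study in essential tremor, and the protocol does not project it onto this trial.
- **The bins follow the design.** The starting step lasts 7 to 14 days, later steps 7 days, and maintenance 12 weeks (SAP 1.2.1 and 1.2.2). The lengths are printed in the labels.
- **The denominator is inferred.** SAP 4.6.2 gives none for these bins; the full Safety Analysis Set is only the natural default.
- **Person-days are not misplaced events.** An event that causes someone to stop usually begins before the last dose and is binned correctly.

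None of this supplies a reason to leave off-drug first onsets unmarked or to omit the number at risk. Both are easy to show.

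**Conclusion.** The point holds as a minor improvement to one descriptive table. The misplacement of off-drug days is complete for last doses up to Day 105 and partial for Days 106–118. Its size depends on when people stop, which the documents do not give. With stops spread over the whole treatment period the mixing is small. The 8–9% in Weeks 3–5 requires every early stop to fall within Days 3–35, and 20% requires all of them on Day 14. Neither should be read as expected, and the documents give no basis for assuming that the arms differ in early stopping.

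The bin-length effect does not depend on stopping, but its illustration rests on an assumed constant hazard and 50% incidence. The denominator effect rests on the inferred Safety Analysis Set default.

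All safety analyses are descriptive (SAP 2.1). No error rate, sample size or efficacy conclusion changes, and the planned listings of dose dates and events would let a reader reclassify individual cases.

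**What to change.** In SAP 4.6.2, for the time-of-first-onset table:

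1. Put first onsets after the last dose in a separate post-treatment category, using the occurrence-based rule already in SAP 4.1.1.3, for early stoppers and completers alike.
2. For each bin and arm, show the number still on treatment and event-free at its start, or an exposure-adjusted rate. Because the event-free number differs by preferred term, the number on treatment can go in the column header and the event-free number in the any-event row.
3. State the percentage denominator explicitly.

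Splitting Week 1 from Week 2 is an optional refinement.

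The cost is SAP wording and a little programming; dose and onset dates are already collected. The drawback is a somewhat longer table.

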#### **Adverse Events Summaries:**

A general overall summary of AEs with the number and percent of study participants who experienced the following types of events will be provided:

- Any TEAE
- Any treatment related TEAE
- Any serious TEAE

- Any TEAE by severity
- Any TEAE leading to permanent study treatment discontinuation
- Any TEAE leading to dose reduction
- Any TEAE leading to dose increase
- Any TEAE leading to dose interruption
- Any AESI

In addition, incidence of AEs will be further summarized by:

- TEAEs by SOC and PT
- TEAEs by PT
- Most common (5% in any arm) TEAEs by SOC and PT
- Most common (5% in any arm) TEAEs by PT without regard to SOC
- Treatment-related TEAEs by SOC and PT
- TEAEs by maximum severity, SOC, and PT
- Serious TEAEs by SOC, and PT
- TEAEs leading to permanent study treatment discontinuation by SOC, and PT
- TEAEs leading to dose increase, reduction and interruption by SOC, and PT
- TEAE by Time of First Onset, SOC, and PT
- AESIs by PT

#### **Adverse Events Listings:**

- All AEs
- Serious AEs
- Adverse events leading to permanent study treatment discontinuation

#### **4.6.3. Additional Safety Analyses**

##### **4.6.3.1. Deaths**

A summary of deaths including primary cause of death will be provided along with a listing. If there are no deaths in the study, produce a summary table and a listing with only the statement “No deaths reported”.

##### **4.6.3.2. Urine Pregnancy Test, Urine Drug Screen and Breath Alcohol Test**

All test assessment results will be listed; in addition, individuals identified with a positive test result will be listed separately.

##### **4.6.3.3. Clinical Laboratory Evaluations**

All clinical laboratory assessments will be summarized by actual received treatment across all study periods.

The continuous clinical laboratory assessments (chemistry, hematology, and urinalysis) will be summarized at each scheduled visit using descriptive statistics. The change from baseline (See Section 4.1.1.1) will be provided at Weeks 5, 9, 13 and 17.

Shift tables will be used to summarize changes in clinical laboratory assessments at Weeks 5, 9, 13 and 17 with respect to baseline.

Laboratory values will be categorized into: 'Normal', 'Low' 'L1', 'High', or 'H1' based on normal range specified in the laboratory manual. L1 and H1 values are predefined alert ranges which correspond to the extreme abnormal lower and higher values.

### **Derivations and Definitions:**

Change from baseline to each post-baseline visit for clinical laboratory value is derived using post-baseline value – baseline value. Change from baseline to a post-baseline visit will not be derived if the laboratory assessment is missing either at baseline or at the corresponding post-baseline visit.

Values for any of the clinical laboratory parameters that are below or above the limit of quantification of the assay (BLoQ or ALoQ), will be summarized using the corresponding BLoQ or ALoQ threshold value. For listings, actual reported values will be used.

Abnormal hepatic/renal function panel values will be identified and flagged for all post-baseline visits if meeting criteria below:

- Aspartate aminotransferase (AST) or Alanine aminotransferase (ALT)  $\geq 3 \times$  Upper Limit of Normal (ULN) and total bilirubin  $\geq 2 \times$  ULN, inclusive (Hy's law)
- AST or ALT  $\geq 3 \times$  ULN and INR  $> 1.5$
- Creatinine  $\geq 1.5 \times$  ULN

### **Clinical Laboratory Summaries:**

- Clinical laboratory results: Chemistry, hematology, and urinalysis, values at each visit and change from baseline for each post-baseline visit.
- Clinical laboratory results: Chemistry, hematology and urinalysis, categorical shifts from baseline to each post-baseline visit

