9.4.5. Safety Analyses

All safety analyses will be performed on the Safety Analysis Set. Safety analyses will be descriptive; no formal statistical testing will be performed. These analyses will be performed as outlined below, with further details provided in the SAP.

Adverse events:

All AEs will be mapped to SOC and PT using the MedDRA classification system. The participant incidence of AEs, AEs related to study intervention, SAEs, AEs leading to discontinuation, and fatal AEs will be summarized. This overall summary will also provide AEs by maximum severity. Note summaries will be provided by treatment group, study period, and time of onset.

The participant incidence of AEs, AEs related to study intervention, and AEs leading to discontinuation will also be presented by SOC and PT. Preferred term summaries may also be provided.

If a participant has multiple events with the same PT occurring in different study periods, the event will be reported for each of those periods. Multiple increases in severity will be counted as 1 AE.

Vital signs:

For each vital sign parameter, summary statistics will be provided for observed and change from Baseline values by scheduled visit.

Physical examinations:

Observed and change from Baseline values for weight will be summarized descriptively by scheduled visit.

12-lead ECG:

Observed and change from Baseline values for ECG intervals will be summarized descriptively. QT abnormalities will be assessed; the number and proportion of participants with values or change from Baseline values exceeding certain thresholds will be tabulated.

Laboratory evaluations:

Observed and change from Baseline laboratory evaluations will be summarized descriptively. Markedly abnormal laboratory findings will be summarized separately.

C-SSRS and QUIP-RS:

The CSSRS parameters and QUIP-RS scores will be summarized descriptively by scheduled visit.

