#### 4.1.2. Visit Windows

All scheduled, unscheduled, and early discontinuation study visits will be summarized based on derived analysis visit window mapping rule outlined per Table 7, which may or may not be the same visit recorded in the database.

For assessments conducted in triplicates, the average value should be mapped. For the Screening visit, the latest assessment conducted prior to Baseline will be used.

If multiple assessments are recorded within a single visit window (including scheduled, unscheduled, repeated, and retest assessments or measurements as well as early discontinuation data), the scheduled assessment should always be prioritized to be mapped to the analysis visit. If there is more than 1 scheduled visit, the following rules can be used to decide which assessment will be mapped to the analysis visit:

- If 2 or more observations occur within the same visit window, then the non-missing observation closest to the scheduled visit day will be used in the analysis.
- If 2 observations are equidistant from the scheduled visit day, then the non-missing observation with the earliest collection date will be used in the analysis.
- If 2 observations are collected on the same day, then the non-missing observation with the earliest collection time will be included in the analysis.

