### **Clinical Laboratory Listings:**

- All clinical laboratory results: chemistry, hematology, and urinalysis
- Abnormal clinical laboratory results: chemistry, hematology, and urinalysis
- Participants with AST or ALT  $\geq 3 \times$  ULN and total bilirubin  $\geq 2 \times$  ULN, or AST or ALT  $\geq 3 \times$  ULN and INR  $> 1.5$
- Participants with Creatinine  $\geq 1.5 \times$  ULN

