#### **4.9. Changes to the Protocol-Planned Analyses**

This SAP added the definition of FAS, defined as “The Full Analysis Set includes all participants who are randomized.” This analysis set will be the primary analysis set for all efficacy analyses.

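### The separate summary of markedly abnormal laboratory findings promised in Protocol 9.4.5 is missing from SAP 4.6.3.3, and SAP 4.9 does not declare the omission

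*SAP*

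**What the plan says.** Protocol 9.4.5 plans descriptive summaries of observed laboratory values and changes from Baseline, and then adds: "Markedly abnormal laboratory findings will be summarized separately". It leaves further detail to the SAP.

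SAP 4.6.3.3 gives that detail in three parts.

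- **Summaries.** There are two. One covers values and change from baseline by visit. The other is "Clinical laboratory results: Chemistry, hematology and urinalysis, categorical shifts from baseline to each post-baseline visit". The categories are Low, L1, Normal, High and H1, where "L1 and H1 values are predefined alert ranges which correspond to the extreme abnormal lower and higher values". Their limits are in the laboratory manual, and results are shown by actual treatment received.
- **Flags.** "Abnormal hepatic/renal function panel values will be identified and flagged for all post-baseline visits if meeting criteria below". The criteria are: (1) AST or ALT at least 3 x ULN with total bilirubin at least 2 x ULN; (2) AST or ALT at least 3 x ULN with INR above 1.5; (3) creatinine at least 1.5 x ULN.
- **Listings.** There are four: all results, abnormal results, one that begins "Participants with AST or ALT" and covers both combined hepatic criteria, and one for creatinine.

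SAP 4.1.2 maps one value to each analysis window. Where a window holds several values, "the scheduled assessment should always be prioritized to be mapped to the analysis visit". The rule extends to unscheduled and repeat draws and to values from an early-discontinuation visit.

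SAP 4.9 is the place for departures from the protocol's analyses. Its only entry begins "This SAP added the definition of FAS" and does not mention laboratory data.

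**The concern.** The protocol names a safety output and the SAP, followed as written, does not produce it or say that it was dropped. It looks like an oversight. In the same SAP, the summary lists for vital signs (4.6.3.4) and ECG (4.6.3.7) each include a markedly abnormal table with numerical thresholds. Laboratory data is the one area for which Protocol 9.4.5 promises a separate summary in those terms, and it has none.

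What is at stake is the safety section of the report. A reader who wants to know how many participants in each arm ever had an extreme laboratory value, or ever met a combined hepatic criterion, would have to count them from listings, without a percentage or a stated denominator. Protocol Appendix 3 treats the liver combinations as possible severe liver injury. Protocol 10.1.5 plans no data monitoring committee, and the sponsor's periodic review is by data listing. The report's tables are therefore the natural place for the comparison between arms, and a result of none in either arm would itself be worth showing.

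**Working it through.** No alpha, power or sample size figure enters this point. The check sets the planned outputs side by side and then follows the window rule through three cases.

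**Planned outputs**

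| Area | Markedly abnormal summary in the SAP |
|---|---|
| Vital signs (4.6.3.4) | 1 |
| ECG (4.6.3.7) | 1 |
| Laboratory (4.6.3.3) | 0 |

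For laboratory data there are 2 summaries and 4 listings. The three flagged criteria appear in 2 of the 4 listings and, as flags, in neither summary. SAP 4.9 declares 0 laboratory changes.

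**Can the shift tables stand in for the missing output?** In part. Read with the categories defined directly after the shift-table sentence, they count L1 and H1 values by arm, for one analyte at one visit. Two things are beyond them:

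- A combined criterion needs two analytes in the same participant (AST or ALT with bilirubin, or with INR). Single-analyte tables cannot show this.
- Counts by visit cannot be added to give the number of participants ever affected, because one participant may be extreme at several visits.

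**Can the adverse event tables stand in?** Also in part. Under Protocol 8.3.4 and Appendix 4, changes that the investigator judges markedly abnormal are recorded as adverse events, or as the diagnosis where there is one. They then reach the SAP 4.6.2 tables by preferred term. That is a judgement-based count, not a count against laboratory criteria.

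**What the window rule does.** In SAP Table 7 the Week 5 window for chemistry and hematology is Days 1 to 48, with target Day 35. Hypothetical cases:

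- (a) An unscheduled extreme value on Day 10, then the scheduled draw on Day 35. Both fall in Days 1 to 48. The scheduled value is kept, and the Day 10 value leaves the shift table.
- (b) The scheduled draw on Day 35, then an early-discontinuation draw on Day 44 with an extreme value. Both fall in Days 1 to 48, and Day 35 is kept. If the early-discontinuation visit is read as scheduled, the closest-to-target rule gives the same answer: |35 - 35| = 0 days against |44 - 35| = 9 days.
- (c) An early-discontinuation draw on Day 20 with no Week 5 draw. It is the only value in the window, so it is kept.

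In (a) and (b) the extreme is lost because the window also holds a scheduled value. An extreme found at the scheduled draw itself is kept, even if a later repeat in that window is normal. Protocol 8 allows repeat and unscheduled samples for safety reasons, so cases like (a) can occur. The documents give no basis for saying how often.

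**The case against.** The strongest reply is that most of the content is already there. L1 and H1 are the SAP's nearest counterpart to markedly abnormal values, and the shift tables count them by arm and visit. In the protocol's own usage the term means investigator judgement (exclusion criterion 27, Section 8.3.4, Appendix 4), and those findings reach the adverse event tables by treatment. One value per window is an ordinary rule for by-visit tables, and a separate listing shows every result. Protocol 9.4.5 does not promise an ever-met count or say that unscheduled values will be used. Entry excludes ALT or AST at or above 2 x ULN, and with about 80 participants per arm two short listings can be counted by hand.

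Much of this stands, and it rules out two readings that a reader might infer.

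- **That no extreme laboratory value is tabulated by arm.** The shift tables do this for single analytes. For creatinine they might even coincide with the SAP's flag, if the H1 limit in the laboratory manual happens to be 1.5 x ULN. The documents do not give that limit.
- **That listing the three flags without tabulating them breaks the protocol commitment.** Neither document says that these criteria are what markedly abnormal means. The SAP says it will flag and list them, and it does.

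The reply does not supply the promised separate summary or declare its absence. It also does not make single-analyte, by-visit counts equivalent to a count of participants ever affected or meeting a combined hepatic criterion.

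**Conclusion.** The point holds as a minor safety-reporting correction. A protocol-specified laboratory summary is missing from SAP 4.6.3.3 and undeclared in 4.9. No planned table counts by arm the participants who ever have an extreme value or who meet the combined hepatic criteria, and the window rule can leave an unscheduled or repeat extreme out of the shift tables.

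The size is one missing table. The number of participants it would show cannot be estimated from the documents and may be zero.

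The verdict rests on two readings: that summarizing separately means an output beyond the value, change and shift tables, and that the shift tables use the L1 and H1 categories. Using L1/H1 and the three flags as the definition is a proposal, not something that the protocol requires.

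A reader might also infer that participants are less well protected. The documents do not support that: adverse event recording, expedited reporting of possible severe liver injury (Protocol Appendix 3) and the listings all capture individual cases. Efficacy and power are not touched.

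**What to change.** Add one table to SAP 4.6.3.3, by actual treatment on the Safety Analysis Set, giving n (%) of participants with:

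- any post-baseline L1 or H1 value, by parameter;
- each of the three hepatic and creatinine criteria met at any post-baseline assessment.

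Use all post-baseline values (scheduled, unscheduled, repeat, early-discontinuation and Safety Follow-up) and do not apply the one-value-per-window rule of SAP 4.1.2 to this table. State that these criteria define the markedly abnormal laboratory findings of Protocol 9.4.5. If the sponsor prefers not to produce the table, declare the omission in SAP 4.9.

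The cost is one extra table and a few lines of SAP text. The flags and the L1/H1 categories are already derived, and no new assessment is needed.
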